**Note: Velocity tracings should be noted on images submitted for Screening Committee review**

**Note: Fine linear signals at peak velocity should not be included in the velocity tracings!**

## 12. Assessment of Aortic Regurgitation

- **Use all echo modalities:** An integrated exam approach using colour flow, pulsed-wave (PW), and continuous-wave (CW) Doppler is used to assess the severity of transvalvular and paravalvular regurgitation.
- **Use four views:** Colour flow Doppler imaging should be performed from the parasternal long and short-axis views, and the apical long-axis and apical 5-chamber views. A recording of the aortic regurgitant signal should be obtained with CW Doppler. If the degree of aortic regurgitation appears more than mild by visual estimate, the velocity in the proximal descending aorta and the abdominal aorta should be recorded with PW Doppler.
- **Severity:** The degree of transvalvular and paravalvular AR will be graded as none, trace, mild, moderate, and severe based on the analysis of the parameters shown in Table 2a.
  - The category of “trace” is used in cases where regurgitation is barely detectable by colour Doppler.
  - Regurgitant signals observed to originate within the stent will be considered transvalvular, and regurgitant signals observed to originate outside the stent will be considered paravalvular.
- Paravalvular regurgitant jets will be characterized by the extent of the aortic regurgitant jet relative to the short axis circumference of the aortic valve (Table 2a- Valve Academic Research Consortium (VARC) Consensus Report for Transcatheter Aortic Valve Implantation (TAVI) and Table 2b. Updated standardized endpoint definitions for transcatheter aortic valve implantation: the VARC-2 consensus document, and Table 3a and b -2008 Focused Update Incorporated Into the ACC/AHA 2006 Guidelines for the Management of Patients With Valvular Heart Disease (published in the October 2008 issues of Journal of the American College of Cardiology and Circulation).

**Table 2a.** Parameters for evaluation of the severity of aortic regurgitation

Prosthetic Aortic Valve Regurgitation Criteria (Central and Paravalvular)			
Parameter	Mild	Moderate	Severe
Valve Structure and Motion Mechanical or bioprosthesis	Usually normal	Usually abnormal†	Usually abnormal†

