The proportion of post-procedure days alive out of hospital against total days alive will be compared between groups at 12 and 24 months. The numerator will be the number of days alive out of hospital, and the denominator will be the number of post-procedure days alive as of the last follow-up date. All hospitalizations will be included in this analysis, including hospitalization for device implant.

In addition, days alive out of hospital will be compared between groups at 12 months and 24 months.

The endpoint will be evaluated using a Bayesian version of a t-test.

11. Quality of Life (QoL) change from baseline at 30 days, 3 months, 6 months, 12 months, 18 months, 24 months, and annually thereafter up to 5 years.

The Kansas City Cardiomyopathy Questionnaire (KCCQ), SF-36, and EuroQoL will be assessed at baseline, 30 days, 6 months, 12 months, 18 months, 24 months, and annually thereafter up to 5 years. SF-36 and EuroQoL will also be assessed at 3 months. All subjects completing the questionnaires will be evaluated and the reasons for missing data will be provided.

The endpoint will be evaluated using a Bayesian version of a t-test.

12. Echocardiographic assessment of prosthetic valve performance at discharge, 6 months, 12 months, 24 months, and annually thereafter up to 5 years using the following measures:

- transvalvular mean gradient
- effective orifice area
- degree of prosthetic aortic valve regurgitation (including transvalvular and paravalvular)

The four echocardiographic measurements will be evaluated at discharge, 6 months, 12 months, 24 months, and annually thereafter up to 5 years. All implanted subjects undergoing echocardiography procedures will be evaluated.

Continuous measures will be evaluated using a Bayesian version of a two-sample t-test. Categorical variables will be evaluated using Bayesian version of a comparison of polytomous outcomes.

Additionally, incidence of moderate/severe aortic insufficiency at discharge will be compared between groups using the Bayesian version of a comparison of proportions.

13. Aortic valve disease related hospitalizations

The number of subjects re-hospitalized after the initial index procedure will be compared at 30 days, 6 months, 12 months, 18 months, 24 months, and annually thereafter up to 5 years.

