### C.11.2 Discrete (Polytomous) Data: Bayesian Version of a Comparison of Proportions

Given the vectors  $\mathbf{p}_t$  and  $\mathbf{p}_c$  of  $k$ -variate proportions for a polytomous outcome, let each be assigned a flat Dirichlet( $\mathbf{1}$ ) prior. The Dirichlet distribution is the multidimensional analog of the Beta distribution. After observing multinomial count data  $\mathbf{Y}_t$  and  $\mathbf{Y}_c$ , the posterior distributions of  $\mathbf{p}_t$  and  $\mathbf{p}_c$  follow Dirichlet( $\mathbf{1}+\mathbf{Y}_t$ ) and Dirichlet( $\mathbf{1}+\mathbf{Y}_c$ ) distributions, respectively. The distribution of the difference  $\mathbf{p}_t - \mathbf{p}_c$  (or ratio) can be easily estimated by drawing a large number of observations (eg, 100,000) from each Dirichlet posterior, and subtracting (or dividing). The marginal posterior probability  $\Pr(p_t^{(i)} - p_c^{(i)} > \delta \mid \text{data})$  for the  $i^{\text{th}}$  component of  $(\mathbf{p}_t - \mathbf{p}_c)$  is estimated as the proportion of these observations where the difference exceeds  $\delta$ . A 95% Bayesian equal-tail credible interval can be calculated from the 2.5th and 97.5th percentiles of the sampled distribution of  $p_t^{(i)} - p_c^{(i)}$ . Posterior probabilities of ratios are similarly calculated from the sampled distribution of  $p_t^{(i)} / p_c^{(i)}$ .

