where  $\pi_{TAVI}$  and  $\pi_{SAVR}$  denote the binary rate of all strokes at 30 days or hospital discharge (if longer). The posterior probability  $P(H | \text{data})$  will be calculated and compared to a threshold of 0.975. The statistical method will be the Bayesian version of a comparison of proportions (see Section C.11).

17. Incidence of moderate/severe aortic insufficiency after TAVI vs. SAVR (secondary objective #12). The hypothesis of interest is

$$H: \pi_{TAVI} < \pi_{SAVR}$$

where  $\pi_{TAVI}$  and  $\pi_{SAVR}$  denote the proportion of subjects with moderate/severe aortic insufficiency at the discharge echo. The posterior probability  $P(H | \text{data})$  will be calculated and compared to a threshold of 0.975. The statistical method will be the Bayesian version of a comparison of proportions (see Section C.11).

18. New pacemaker implant rate for TAVI at 30 days or hospital discharge, whichever is longer (secondary objective #7). The hypothesis of interest is

$$H: \pi_{TAVI} < 30\%$$

where  $\pi_{TAVI}$  denote the binary rate of new pacemaker implants for TAVI at 30 days or hospital discharge (if longer). The posterior probability  $P(H | \text{data})$  will be calculated and compared to a threshold of 0.975. The statistical method will be the Bayesian version of a comparison of proportions (see Section C.11).

Other than the hierarchical testing procedure described above, no further multiplicity adjustments will be made in the analyses of the secondary endpoints. Summary data from other secondary objectives, such as device success and procedural success from secondary objectives #20 and #21, respectively, may be provided in the device labeling. However, no claims of statistical significance or other statistical inference will be made.

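### The ordered aortic regurgitation grade is compared one grade at a time, so the full-scale comparison has no single direction and nothing after discharge stands alone to say which arm leaks less

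*Combined protocol and SAP*

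**What the plan says.** The echocardiography guidelines (Appendix R.7, section 12) set the scale: "The degree of transvalvular and paravalvular AR will be graded as none, trace, mild, moderate, and severe".

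SAP Version 6.0, C.10 item 12, lists the degree of prosthetic regurgitation among its valve performance measures. They are compared at discharge, at 6, 12 and 24 months, and yearly to 5 years. For non-continuous measures it says: "Categorical variables will be evaluated using Bayesian version of a comparison of polytomous outcomes".

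C.11.2 defines that method. Each arm's vector of proportions gets a flat Dirichlet prior. "The marginal posterior probability" is then taken for one component at a time and "is estimated as the proportion of these observations where the difference exceeds" a value delta. Of the interval it says "A 95% Bayesian equal-tail credible interval can be calculated from the" 2.5th and 97.5th percentiles, again per component. C.11.2 gives no ordering, cumulative proportion, overall summary, value of delta or decision threshold.

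Item 12 adds one directional comparison: "Additionally, incidence of moderate/severe aortic insufficiency at discharge will be compared between groups using the Bayesian version of a comparison of proportions". In C.12.1 this is labeling objective #17, a superiority test at 0.975 whose two rates "denote the proportion of subjects with moderate/severe aortic insufficiency at the discharge echo".

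**The concern.** None, trace, mild, moderate and severe run from best to worst. Comparing each grade with all the others discards that order. For the middle grades the result has no good or bad direction: more mild leak in one arm may come from fewer subjects with none, which is worse, or from fewer with moderate, which is better. Each visit yields five probabilities that may point different ways, and the plan does not say which one answers the question.

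The SAP keeps order elsewhere. NYHA class, also an ordered grade, is scored as classes changed and given one directional comparison (C.10 item 8; C.12.1 #3). A rank-based method is defined in C.11.5 but is not assigned to regurgitation.

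At stake is how clearly a between-arm comparison lasting five years can be read, and the freedom to choose afterwards which grade to emphasise. No primary result or labeling claim depends on it.

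**Working it through.** **Inputs.** The documents give five grades, seven visits (discharge, 6, 12 and 24 months, 3, 4 and 5 years) and 1600 mITT subjects randomized 1:1, so 1600 / 2 = 800 per arm. They give no grade distribution, effect size, echo count, power or threshold for this comparison, so there is no figure of the plan's own to reproduce. Assumed here: 650 echoes per arm, and SAVR grades (none/trace/mild/moderate/severe, %) of D1 = 40/30/25/4.5/0.5, D2 = 60/25/13/1.8/0.2 and D3 = 25/35/32/7/1.

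**1. A single grade has no direction.** Define the ordinal contrast as C = P(TAVI grade lower) - P(TAVI grade higher). If d_i is the TAVI minus SAVR difference in grade i, then C = sum of d_i x s_i, where s_i = P(SAVR grade above i) - P(SAVR grade below i). Under D1, s = 0.600, -0.100, -0.650, -0.945, -0.995.
- Three points move from none to mild: C = -0.03 x 0.600 + 0.03 x (-0.650) = -0.0375. TAVI is worse.
- Three points move from moderate to mild: C = 0.03 x (-0.650) - 0.03 x (-0.945) = +0.0089. TAVI is better.

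The difference in mild is +3 points both times. The cumulative proportions separate the two cases: at-least-mild goes from 30% to 33% in the first, and at-least-moderate from 5% to 2% in the second.

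**2. False differences if each interval is read as a finding.** This reading rule is an assumption; C.11.2 sets none. Five independent 95% intervals would give 1 - 0.95^5 = 0.226. The grades are not independent, so C.11.2 was simulated with identical arms. At least one interval excluded zero in 0.183, 0.164 and 0.197 of trials (D1-D3, 650 per arm), and in 0.180, 0.161 and 0.220 with 550 per arm. The ordinal contrast was flagged in 0.038-0.050. A separate simulation with other distributions (60/25/12/2.5/0.5 and 40/30/22/7/1; 500 and 800 per arm) gave 18-21% against 4-6% for a rank test. Across all visits there are 5 x 7 = 35 intervals for each leak location.

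**3. Power under a uniform shift (common odds ratio 1.3, 650 per arm).** A hand check for D1: TAVI grades become 33.9/30.3/29.4/5.8/0.6 and C = -0.0787. Its standard error is about sqrt(2 x sum of p_i s_i^2 / 650) = sqrt(2 x 0.298 / 650) = 0.0303. Then z = 0.0787 / 0.0303 = 2.60, and power is Phi(2.60 - 1.96) = 0.74. Simulation gives:

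| Distribution | Ordinal contrast | Any grade, 99% intervals (error-matched) | Any grade, 95% intervals (unadjusted) |
|---|---|---|---|
| D1 | 0.74 | 0.49 | 0.78 |
| D2 | 0.65 | 0.44 | 0.71 |
| D3 | 0.71 | 0.43 | 0.71 |

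**4. Power when only the top grades differ.** Three points move from mild into moderate/severe. Under D1, treating all three as moderate, C = -0.03 x (-0.650) + 0.03 x (-0.945) = -0.0089, about 0.3 standard errors. Simulated power of the ordinal contrast is 0.05-0.07. The moderate/severe proportion has 0.55, 0.83 and 0.44 (D1-D3).

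**5. What covers regurgitation after discharge.** Moderate or severe regurgitation enters the MAE component of prosthetic valve dysfunction (item 3) and the valve-related dysfunction parts of items 5 and 6. All are wider than regurgitation. Item 22 covers the TAVI arm only.

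**The case against.** The strongest objection is that the question that matters clinically is already answered. The documents use moderate/severe as the relevant cut throughout, that cut is tested directionally at discharge, and the test sits in the labeling hierarchy. A reader might infer from the grade-by-grade method that the plan never says which valve leaks less. That is wrong at discharge. What remains is the full scale and every later visit. Objective #17 is also 13th of the 14 ordered tests in its subfamily (#5 to #18), so its formal test may not be reached.

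A reader might also take 16-22% as an error rate of the trial. It is not: C.11.2 sets no flagging rule, and C.12 says analyses outside the hierarchy will not support labeling claims.

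A third tempting inference is that the plan simply loses power. The table does not support it: an unadjusted any-grade reading has as much power as the ordinal contrast or more, at a false-difference rate near 20%. The loss appears only when error is matched and the shift is uniform. Step 4 shows the reverse when only the top grades move.

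It is also fair that an ordinal summary is driven largely by movement between none and trace, which hold 60-85% of subjects in D1-D3, while Appendix R.7 uses trace for leak that can barely be detected. This stands as a reason not to report the ordinal contrast alone.

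**Conclusion.** The point holds in a limited form. Item 12 together with C.11.2 ignores the order of the regurgitation grade and yields no single directional result for the full scale at any visit. After discharge there is no stand-alone directional comparison of regurgitation between the arms. Both statements follow from the text alone.

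The sizes depend on assumed grade distributions, echo counts and effects, and the false-difference figure also on a reading rule the SAP does not contain. On those terms the rate is about 16-22% per visit against about 5%. The error-matched gain under a uniform shift is 21 to 28 points (0.65 - 0.44 = 0.21 for D2; 0.71 - 0.43 = 0.28 for D3). There is no gain, and a clear loss against the moderate/severe proportion, if only the top grades differ.

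This is a worthwhile improvement to a secondary analysis that supports no claim. It does not touch the primary endpoint, the sample size or the type I error of the labeling hierarchy.

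**What to change.** In C.10 item 12, keep the Dirichlet(1) posteriors of C.11.2 and state that at every item 12 visit the regurgitation comparison will report, from the same draws:

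- the TAVI minus SAVR difference in the proportion with at least mild and with at least moderate regurgitation, each with the posterior probability that it is below zero and a 95% credible interval;
- one ordinal contrast, P(TAVI grade lower) minus P(TAVI grade higher), with the posterior probability that it exceeds zero and a 95% credible interval.

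State that the ordinal contrast is always shown beside the cumulative proportions, since at-least-moderate covers the pattern the contrast misses. Keep the per-grade percentages as description. Leave the discharge moderate/severe test and objective #17 as they are.

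The cost is SAP wording and a few lines of code on draws already generated, with no new data. The downside is a few more reported quantities per visit and one summary that is insensitive to shifts confined to the top grades.

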## C.10 Secondary Endpoints

The following secondary endpoints will be compared between TAVI and SAVR subject cohorts using the appropriate Bayesian version of analysis for comparing proportions and continuous variables as described below:

1. Incidence of Major Adverse Cardiovascular and Cerebrovascular Events (MACCE) at 30 days, 6 months, 12 months, 18 months, 24 months, and annually thereafter up to 5 years. MACCE is defined as a composite of:

- All-cause death
- Myocardial infarction (MI)
- All stroke, and
- Reintervention (defined as any cardiac surgery or percutaneous reintervention catheter procedure that repairs, otherwise alters or adjusts, or replaces a previously implanted valve)

MACCE-incidence estimates will be provided for the two treatment groups at 30 days, 6 months, 12 months, 18 months, 24 months, and annually thereafter up to 5 years. The statistical method will be the Bayesian version of a comparison of proportions (with predictions).

Additionally, incidence of MACCE will be compared at 30 days or hospital discharge, whichever is later. The statistical method will be the Bayesian version of a comparison of proportions

2. The occurrence of individual MACCE components at 30 days, 6 months, 12 months, 18 months, 24 months, and annually thereafter up to 5 years.

MACCE components will be summarized and their incidence estimates provided at 30 days, 6 months, 12 months, 18 months, 24 months, and annually thereafter up to 5 years. The statistical method will be the Bayesian version of a comparison of proportions (with predictions).

3. Major Adverse Events (MAE) and individual components of MAE at 30 days, 6 months, 12 months, 18 months, 24 months, and annually thereafter up to 5 years.

Major adverse event (MAE) includes:

- MACCE
- Acute kidney Injury
- Cardiac tamponade
- Prosthetic valve dysfunction – including moderate or severe aortic regurgitation
- Cardiogenic shock
- Prosthetic valve endocarditis
- Life-threatening, disabling or major bleeding
- Major vascular complication
- Cardiac perforation
- Valve malpositioning

MAE events and individual components of MAE will be summarized and the incidence of MAEs will be provided at 30 days, 6 months, 12 months, 18 months, 24 months, and annually thereafter up to 5 years. The statistical method will be the Bayesian version of a comparison of proportions (with predictions).

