Additionally, incidence of major vascular complications and incidence of major or life-threatening bleeding events at 30 days or hospital discharge, whichever is longer, will also be compared using the Bayesian version of a comparison of proportions.

4. Incidence of Early safety at 30 days defined as a composite of:

- All-cause mortality
- All stroke (disabling and non-disabling)
- Life-threatening bleeding
- Acute kidney injury—Stage 2 or 3 (including renal replacement therapy)
- Coronary artery obstruction requiring intervention
- Major vascular complication
- Valve-related dysfunction requiring repeat procedure (BAV, TAVI, or SAVR)
- All-cause death

Early safety composite endpoint-incidence estimates will be provided for the two treatment groups at 30 days. The statistical method will be the Bayesian version of a comparison of proportions.

5. Incidence of Clinical Efficacy (after 30 days) at 6 months, 12 months, 18 months, 24 months and annually thereafter up to 5 years. Clinical efficacy defined as a composite of:
- All-cause mortality
  - All stroke (disabling and non-disabling)
  - Requiring hospitalizations for valve-related symptoms or worsening congestive heart failure
  - NYHA class III or IV
  - Valve-related dysfunction (mean aortic valve gradient  $\geq 20$  mmHg, EOA  $\leq 0.9$ - $1.1$  cm^2 and/or DVI  $< 0.35$  m/s, AND/OR moderate or severe prosthetic valve regurgitation\*)

Clinical efficacy estimates will be provided for the two treatment groups at 6 months, 12 months, 18 months, 24 months and annually thereafter up to 5 years. The statistical method will be the Bayesian version of a comparison of proportions (with predictions).

\*Refers to VARC-2 definitions

6. Incidence of Time-Related Safety at 30 days, 6 months, 12 months, 18 months, 24 months and annually thereafter up to 5 years. Time-Related Safety defined as a composite of:
- Structural valve deterioration:
    - Valve-related dysfunction (mean aortic valve gradient  $\geq 20$  mmHg, EOA  $\leq 0.9$ - $1.1$  cm^2 and/or DVI  $< 0.35$  m/s, AND/OR moderate or severe prosthetic valve regurgitation\*)
    - Requiring repeat procedure (TAVI or SAVR)
  - Prosthetic valve endocarditis
  - Prosthetic valve thrombosis
  - Thromboembolic events (e.g. stroke)
  - VARC bleeding, unless clearly unrelated to valve therapy (e.g. trauma)

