Incidence of recurrent hospitalization will be provided at 30 days, 6 months, 12 months, 18 months, 24 months, and annually thereafter up to 5 years. The statistical method will be the Bayesian version of a comparison of proportions (with predictions).

14. Cardiovascular deaths and valve-related deaths

The number of subjects experiencing cardiovascular deaths and valve-related deaths at 30 days, 6 months, 12 months, 18 months, 24 months, and annually thereafter up to 5 years. Incidences will be compared between groups. The statistical method will be the Bayesian version of a comparison of proportions (with predictions).

15. Strokes and TIAs

The number of subjects with strokes (of any severity) and TIAs at 30 days, 6 months, 12 months, 18 months, 24 months, and annually thereafter up to 5 years. A separate analysis will be performed for each of the following:

- a composite of all strokes and TIAs
- disabling strokes only
- non-disabling strokes only
- TIAs only

The statistical method will be the Bayesian version of a comparison of proportions (with predictions).

Additionally, incidence of all strokes at 30 days or hospital discharge, whichever is longer, will be compared between groups using the Bayesian version of a comparison of proportions.

16. Peri-procedural Neurological Injury (Stroke, TIA, Encephalopathy)

For each treatment group, the proportion of subjects with a neurologic injury (stroke, TIA, or encephalopathy) at discharge or at 7 days post-index procedure (whichever occurs first) will be calculated. The numerator will be the number of subjects with a neurologic injury (stroke, TIA, or encephalopathy) at discharge or at 7 days post-index procedure (whichever occurs first), and the denominator will be the number of subjects in that treatment group. Results will also be presented separately for disabling stroke, non-disabling stroke, TIA, and encephalopathy. Proportions will be compared between groups using Bayesian version of a comparison of proportions.

17. Index procedure related MAEs

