**Rationale for Delta:** A difference less than 0.375 for NYHA classification is not considered clinically relevant for the SURTAVI Steering Committee.

4. Change in Kansas City Cardiomyopathy Questionnaire (KCCQ) score from baseline to 30 days (non-inferiority): TAVI vs. SAVR (secondary objective #11). The hypothesis of interest is

$$H: \mu_{TAVI} > \mu_{SAVR} - 5$$

where  $\mu_{TAVI}$  and  $\mu_{SAVR}$  denote the mean improvements in the KCCQ score from baseline to 30 days. For subjects with KCCQ score at both baseline and 30 days, the improvement in KCCQ will be calculated as  $\text{KCCQ}_{30\text{day}} - \text{KCCQ}_{\text{baseline}}$ . The objective will be evaluated using a Bayesian version of a two-sample t-test (see Section C.11). The posterior probability  $P(H | \text{data})$  will be calculated and compared to a threshold of 0.95.

**Rationale for Delta:** A 5 point improvement or decrease in KCCQ is the minimum difference that is clinically relevant. (Spertus J, et al, "Monitoring clinical changes in patients with heart failure: A comparison of methods," American Heart Journal 2005;150:710-715.)

5. Length of index procedure hospital stay after TAVI vs. SAVR (secondary objective #18). The hypothesis of interest is

$$H: \mu_{TAVI} < \mu_{SAVR}$$

where  $\mu_{TAVI}$  and  $\mu_{SAVR}$  denote the mean length of index hospital stay. The objective will be evaluated using a Bayesian version of a two-sample t-test (see Section C.11). The posterior probability  $P(H | \text{data})$  will be calculated and compared to a threshold of 0.975.

6. Transvalvular mean gradient at 12 months (superiority): TAVI vs. SAVR (secondary objective #12). The hypothesis of interest is

$$H: \mu_{TAVI} < \mu_{SAVR}$$

where  $\mu_{TAVI}$  and  $\mu_{SAVR}$  denote the average mean gradient at 12 months, measured in mmHg. This objective will be evaluated using a Bayesian version of a two-sample t-test (see Section C.11). The posterior probability  $P(H | \text{data})$  will be calculated and compared to a threshold of 0.975.

7. Effective orifice area at 12 months (superiority): TAVI vs. SAVR (secondary objective #12). The hypothesis of interest is

$$H: \mu_{TAVI} > \mu_{SAVR}$$

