12. Change in EQ-5D from baseline to 3 months: TAVI vs. SAVR (secondary objective #11). The hypothesis of interest is

$$H: \mu_{TAVI} > \mu_{SAVR}$$

where  $\mu_{TAVI}$  and  $\mu_{SAVR}$  denote the mean improvements in the EQ-5D from baseline to 3 months. The objective will be evaluated using a Bayesian version of a two-sample t-test (see Section C.11). The posterior probability  $P(H | \text{data})$  will be calculated and compared to a threshold of 0.975.

13. Incidence of MACCE at 30 days or hospital discharge, whichever is longer: TAVI vs. SAVR (secondary objective #1). The hypothesis of interest is

$$H: \pi_{TAVI} < \pi_{SAVR}$$

where  $\pi_{TAVI}$  and  $\pi_{SAVR}$  denote the binary rate of MACCE at 30 days or hospital discharge (if longer). The posterior probability  $P(H | \text{data})$  will be calculated and compared to a threshold

of 0.975. The statistical method will be the Bayesian version of a comparison of proportions (see Section C.11).

14. Incidence of major vascular complication at 30 days or hospital discharge, whichever is longer: TAVI vs. SAVR (secondary objective #3). The hypothesis of interest is

$$H: \pi_{TAVI} < \pi_{SAVR}$$

where  $\pi_{TAVI}$  and  $\pi_{SAVR}$  denote the binary rate of major vascular complications at 30 days or hospital discharge (if longer). The posterior probability  $P(H | \text{data})$  will be calculated and compared to a threshold of 0.975. The statistical method will be the Bayesian version of a comparison of proportions (see Section C.11).

15. Incidence of major or life-threatening bleeding events at 30 days or hospital discharge, whichever is longer: TAVI vs. SAVR (secondary objective #3). The hypothesis of interest is

$$H: \pi_{TAVI} < \pi_{SAVR}$$

where  $\pi_{TAVI}$  and  $\pi_{SAVR}$  denote the binary rate of major or life-threatening bleeding events at 30 days or hospital discharge (if longer). The posterior probability  $P(H | \text{data})$  will be calculated and compared to a threshold of 0.975. The statistical method will be the Bayesian version of a comparison of proportions (see Section C.11).

16. Incidence of all strokes at 30 days or hospital discharge, whichever is longer: TAVI vs. SAVR (secondary objective #15). The hypothesis of interest is

$$H: \pi_{TAVI} < \pi_{SAVR}$$

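### Secondary endpoint 16 stops counting neurological injury at discharge, so an arm that goes home sooner is observed for less time and looks safer at equal risk

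*Combined protocol and SAP*

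**What the plan says.** All references are to the SAP at version 6.0 (based on CIP version 12.0).

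- **Window.** C.10, endpoint 16: the proportion with a neurologic injury "at discharge or at 7 days post-index procedure (whichever occurs first) will be calculated".
- **Denominator.** Same entry: "the denominator will be the number of subjects in that treatment group".
- **Comparison.** Same entry: "Proportions will be compared between groups using Bayesian version of a comparison of proportions". That method (C.11.1) is a beta-binomial on numbers of subjects. It has no term for time observed.
- **Length of stay.** C.12.1, objective 5: "Length of index procedure hospital stay after TAVI vs. SAVR (secondary objective #18", tested as superiority of TAVI at a threshold of 0.975. No stay in days is given for either arm.
- **Other windows that mention discharge.** Four comparisons run to the later of day 30 and discharge: "incidence of MACCE will be compared at 30 days or hospital discharge, whichever is later"; "incidence of major vascular complications and incidence of major or life-threatening bleeding events at 30 days or hospital discharge, whichever is longer"; and "incidence of all strokes at 30 days or hospital discharge, whichever is longer, will be compared between groups". These are objectives 13 to 16 in C.12.1.
- **Fixed-window analyses.** MACCE and its components, MAE and its components, and strokes and TIAs are also analysed at a fixed 30 days (endpoints 1, 2, 3 and 15). Endpoint 16 has no fixed 7-day version. Encephalopathy is not part of endpoint 15.

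**The concern.** A proportion compared between randomized arms should count events over the same period in both. Endpoint 16 does not ensure this. A subject discharged on day 4 is counted to day 4, while a subject still in hospital on day 7 is counted to day 7, and both contribute one full unit to the denominator. Discharge date is itself a consequence of treatment, and the plan hypothesises that it differs between the arms in a known direction.

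At stake is the reading of a between-arm comparison of neurological safety. A lower TAVI figure could reflect fewer injuries, fewer days of looking, or both, and the planned analysis cannot separate them. For stroke and TIA a reader can turn to the fixed 30-day results. For encephalopathy nothing else is planned.

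**Working it through.** The documents state no figure on this point, so there is none to reproduce. The check asks what endpoint 16 would show if the true risk were identical in the two arms.

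**Inputs from the SAP:** window = min(discharge day, 7); 1600 mITT subjects randomized 1:1 (C.4.2), so about 800 per arm.

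**Assumptions, because the documents are silent:** stay is lognormal with log-SD 0.6 and independent of event risk; the true 7-day rate is 6% in both arms (varied from 4% to 10%); event timing within the week is front-loaded with a half-life of 1 or 2 days, or follows a constant hazard. A superiority finding is taken as one-sided 0.025 by normal approximation.

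**Step 1: mean window.** For median stay *m*, E[min(S,7)] = m·exp(0.18)·Φ((ln(7/m) − 0.36)/0.6) + 7·[1 − Φ(ln(7/m)/0.6)].

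- m = 7: 7 × 1.197 × 0.274 + 7 × 0.5 = 2.30 + 3.50 = 5.80 days
- m = 5: 5 × 1.197 × 0.484 + 7 × 0.287 = 2.90 + 2.01 = 4.91 days
- m = 4 and m = 8, by the same formula: 4.25 and 6.09 days

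**Step 2: share of 7-day events captured.** Under a constant hazard this is the mean window divided by 7. With half-life *h* it is the mean of (1 − 2^(−min(S,7)/h)) / (1 − 2^(−7/h)).

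**Step 3: apparent risk ratio** = share captured in TAVI / share captured in SAVR. The true rate cancels. For example, under a constant hazard with 5 against 7 days, 4.91/5.80 = 0.85. With a 6% true rate the arms would show 6% × 0.702 = 4.21% and 6% × 0.828 = 4.97%, a gap of 0.76 points.

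| Median stay, TAVI vs SAVR | Event timing | Captured, TAVI / SAVR | Apparent RR | Gap at 6% (points) | Chance of a false superiority finding |
|---|---|---|---|---|---|
| 7 vs 7 | any | equal | 1.00 | 0 | 2.5% |
| 5 vs 7 | half-life 1 day | 0.935 / 0.970 | 0.96 | 0.21 | 3.8% |
| 5 vs 7 | half-life 2 days | 0.852 / 0.922 | 0.92 | 0.42 | 5.7% |
| 5 vs 7 | constant | 0.702 / 0.828 | 0.85 | 0.76 | 10.8% |
| 4 vs 8 | half-life 1 day | 0.901 / 0.979 | 0.92 | 0.47 | 6.0% |
| 4 vs 8 | half-life 2 days | 0.790 / 0.943 | 0.84 | 0.92 | 12.8% |
| 4 vs 8 | constant | 0.606 / 0.869 | 0.70 | 1.58 | 33.5% |

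Across true rates of 4% to 10%, the gap in these two stay scenarios runs from 0.14 to 2.62 points. With a common 7-day window the ratio is 1.00 and the chance is 2.5% throughout.

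**Step 4: the four comparisons with a 30-day floor.** Every subject is counted for at least 30 days, so only stays beyond day 30 add time. Rate = base + (share still in hospital after day 30) × (chance of a first event in the extension) × (1 − base). The base is 5.9%, the 30-day all-stroke rate in the SAVR intermediate-risk cohort (Appendix G.4, Table 16). The other inputs are assumed.

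- 0.5% vs 1% in hospital, 5% to 10% chance: 0.005 × 0.05 × 0.941 = 0.02 points, up to 0.05 points; false superiority 2.6% to 2.7%
- 1% vs 3%, 10% chance: 0.02 × 0.10 × 0.941 = 0.19 points; RR 0.97; 3.6%
- 1% vs 5%, 30% chance, an extreme case: 0.04 × 0.30 × 0.941 = 1.13 points; RR 0.85; 14%

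**The case against.** **The endpoint carries little decision weight.** It is not in the C.12 hierarchy, and the SAP says that objectives outside it will not support labeling claims. This stands and limits the consequence. The comparison will still be reported.

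**Stroke and TIA are already compared at a fixed 30 days.** True for endpoint 15. It gives no 7-day answer, and it leaves encephalopathy without any fixed-window counterpart.

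**The window plausibly follows an in-hospital assessment.** The post-procedure echocardiogram (Appendix R.7, section 2) has a similar limit: by discharge, but no later than 7 days. An endpoint tied to a pre-discharge examination is a recognisable choice. That explains the definition but does not equalise observation time. The neurological assessment schedule and event-reporting rules belong to the main protocol body, which is not in the text reviewed here.

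**The plan does not say that TAVI stays will be shorter.** Correct: objective 5 is a hypothesis under test, and the distortion depends on the stays observed. If they are alike, it vanishes. If events cluster in the first day or two, it is small (RR 0.92 to 0.96 with a 1-day half-life).

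**A stronger reading.** A reader might infer that all five comparisons with a discharge-dependent window favour TAVI by construction. The documents do not support that. For objectives 13 to 16 the window is the longer of the two limits, so both arms have the same 30 days except in subjects still in hospital afterwards. Under the sequential rule in C.12 these tests are reached only after objective 5 has passed, but a shorter mean stay says nothing certain about the share beyond day 30, and no such share is given. The endpoints are per-subject, so a long-stay patient who has already had the event adds nothing.

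**Conclusion.** The point holds for endpoint 16. Its window closes at discharge, its denominator does not change, and its method ignores time observed. If TAVI subjects go home sooner, equal true risk will be reported as a lower TAVI rate. For assumed median stays between 5 against 7 and 4 against 8 days, the apparent ratio is about 0.70 to 0.96. Where it falls depends mostly on how early in the week the events occur. The stays, their spread, their independence from risk and the event timing are all assumptions.

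A reported secondary comparison is affected. No labeling claim is. For objectives 13 to 16, a plausible effect is about 0.02 to 0.2 points with its direction not established. Which 30-day version carries the claim is largely a matter of preference.

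**What to change.** 1. In C.10, endpoint 16, count stroke, TIA and encephalopathy with onset through day 7 after the index procedure in every subject, regardless of discharge date. Apply the same window to the components already listed for separate presentation.
2. Keep the discharge-or-day-7 version as a sensitivity analysis, and report observation time by arm beside it.
3. Leave objectives 13 to 16 as they are, and show the planned fixed 30-day results for the same events alongside them.

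The cost is SAP wording. Stroke and TIA must in any case be ascertained to 30 days for endpoint 15. The downside is that mild encephalopathy arising after discharge may be under-reported, so some imbalance could remain in that component. The sponsor should confirm from the protocol's reporting rules that onset dates for encephalopathy are collected after discharge.
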